## **5.2.5 Other safety parameters**

### **5.2.5.1 Continuous ECG monitoring**

Cardiac rhythm (including heart rate) will be monitored by means of continuous bedside monitoring (Mortara Surveyor S12) predose and about 4 h following tyramine administration.

This continuous ECG monitoring supports the early detection of adverse events such as clinically relevant bradycardia, tachycardia, or arrhythmia at the trial site. Beyond this clinical evaluation at the trial site, no further data collection or analyses will be performed based on continuous ECG monitoring.

ECG data from continuous ECG recording will not transferred to the clinical trial database. Abnormal findings during continuous ECG recording will be recorded as AEs if judged clinically relevant by the Investigator.

## **5.2.6 Assessment of adverse events**

### **5.2.6.1 Definitions of adverse events**

#### **5.2.6.1.1 Adverse event**

An adverse event (AE) is defined as any untoward medical occurrence in a patient or clinical investigation subject administered a medicinal product and which does not necessarily have to have a causal relationship with this treatment.

An AE can therefore be any unfavourable and unintended sign (including an abnormal laboratory finding), symptom, or disease temporally associated with the use of a medicinal product, whether or not considered related to the medicinal product.

The following should also be recorded as an AE in the CRF and BI SAE form (if applicable):

- Worsening of the underlying disease or of other pre-existing conditions
- Changes in vital signs, ECG, physical examination, and laboratory test results, if they are judged clinically relevant by the investigator

If such abnormalities already pre-exist prior to trial inclusion, they will be considered as baseline conditions and should be collected in the eCRF only.

#### 5.2.6.1.2 Serious adverse event

A serious adverse event (SAE) is defined as any AE which fulfils at least one of the following criteria:

- Results in death
- Is life-threatening, which refers to an event in which the patient was at risk of death at the time of the event; it does not refer to an event that hypothetically might have caused death if more severe
- Requires inpatient hospitalisation
- Requires prolongation of existing hospitalisation
- Results in persistent or significant disability or incapacity
- Is a congenital anomaly/birth defect
- Is deemed serious for any other reason if it is an important medical event when based upon appropriate medical judgment which may jeopardise the patient and may require medical or surgical intervention to prevent one of the other outcomes listed in the above definitions. Examples of such events are intensive treatment in an emergency room or at home for allergic bronchospasm, blood dyscrasias or convulsions that do not result in hospitalisation or development of dependency or abuse

#### 5.2.6.1.3 AEs considered ‘Always Serious’

Cancers of new histology and exacerbations of existing cancer must be classified as a serious event regardless of the time since discontinuation of the trial medication and must be reported as described in [Section 5.2.6.2](#), subsections ‘AE Collection’ and ‘AE reporting to sponsor and timelines’.

In accordance with the European Medicines Agency initiative on Important Medical Events, Boehringer Ingelheim has set up a list of further AEs, which, by their nature, can always be considered to be ‘serious’ even though they may not have met the criteria of an SAE as defined above.

The latest list of ‘Always Serious AEs’ can be found in the eDC system, an electronic data capture system which allows the entry of trial data at the trial site. These events should always be reported as SAEs as described above.

#### 5.2.6.1.4 Adverse events of special interest

The term adverse events of special interest (AESI) relates to any specific AE that has been identified at the project level as being of particular concern for prospective safety monitoring and safety assessment within this trial, e.g. the potential for AEs based on knowledge from other compounds in the same class. AESIs need to be reported to the sponsor’s Pharmacovigilance Department within the same timeframe that applies to SAEs, please see [Section 5.2.6.2.2](#).

The following are considered as AESIs:

- Hepatic injury

A hepatic injury is defined by the following alterations of hepatic laboratory parameters:

- o An elevation of AST (aspartate transaminase) and/or ALT (alanine transaminase)  $\geq 3$ -fold ULN combined with an elevation of total bilirubin  $\geq 2$ -fold ULN measured in the same blood sample, or
- o Aminotransferase (ALT, and/or AST) elevations  $\geq 10$  fold ULN

These lab findings constitute a hepatic injury alert and the subjects showing these lab abnormalities need to be followed up according to the 'DILI checklist' provided via eDC. In case of clinical symptoms of hepatic injury (icterus, unexplained encephalopathy, unexplained coagulopathy, right upper quadrant abdominal pain, etc.) without lab results (ALT, AST, total bilirubin) available, the Investigator should make sure that these parameters are analysed, if necessary in an unscheduled blood test. Should the results meet the criteria of hepatic injury alert, the procedures described in the DILI checklist should be followed.

#### 5.2.6.1.5 Intensity (severity) of AEs

The intensity (severity) of the AE should be judged based on the following:

Mild: Awareness of sign(s) or symptom(s) that is/are easily tolerated

Moderate: Sufficient discomfort to cause interference with usual activity

Severe: Incapacitating or causing inability to work or to perform usual activities.

#### 5.2.6.1.6 Causal relationship of AEs

Medical judgment should be used to determine the relationship, considering all relevant factors, including pattern of reaction, temporal relationship, de-challenge or re-challenge, confounding factors such as concomitant medication, concomitant diseases and relevant history.

Arguments that may suggest that there is a reasonable possibility of a causal relationship could be:

- The event is consistent with the known pharmacology of the drug
- The event is known to be caused by or attributed to the drug class
- A plausible time to onset of the event relative to the time of drug exposure
- Evidence that the event is reproducible when the drug is re-introduced
- No medically sound alternative aetiologies that could explain the event (e.g. pre-existing or concomitant diseases, or co-medications)
- The event is typically drug-related and infrequent in the general population not exposed to drugs (e.g. Stevens-Johnson syndrome)
- An indication of dose-response (i.e. greater effect size if the dose is increased, smaller effect size if dose is reduced)

Proprietary confidential information © 2020 Boehringer Ingelheim International GmbH or one or more of its affiliated companies

Arguments that may suggest that there is no reasonable possibility of a causal relationship could be:

- No plausible time to onset of the event relative to the time of drug exposure is evident (e.g. pre-treatment cases, diagnosis of cancer or chronic disease within days / weeks of drug administration; an allergic reaction weeks after discontinuation of the drug concerned)
- Continuation of the event despite the withdrawal of the medication, taking into account the pharmacological properties of the compound (e.g. after 5 half-lives). Of note, this criterion may not be applicable to events whose time course is prolonged despite removing the original trigger
- Additional arguments amongst those stated before, like alternative explanation (e.g. situations where other drugs or underlying diseases appear to provide a more likely explanation for the observed event than the drug concerned)
- Disappearance of the event even though the trial drug treatment continues or remains unchanged

#### 5.2.6.2 Adverse event collection and reporting

##### 5.2.6.2.1 AE collection

Upon enrolment into a trial, the subject's baseline condition is assessed (for instance, by documentation of medical history/concomitant diagnoses), and relevant changes from baseline are noted subsequently.

Subjects will be required to report spontaneously any AEs as well as the time of onset, end time, and intensity of these events. In addition, each subject will be regularly assessed by the medical staff throughout the clinical trial and whenever the investigator deems necessary. As a minimum, subjects will be questioned for AEs (and concomitant therapies) at the time points indicated in the [Flow Chart](#). Assessment will be made using non-specific questions such as 'How do you feel?'. Specific questions will be asked wherever necessary in order to more precisely describe an AE.

A carefully written record of all AEs shall be kept by the investigator in charge of the trial. Records of AEs shall include data on the time of onset, end time, intensity of the event, and any treatment or action required for the event and its outcome.

The following must be collected and documented on the appropriate CRF(s) by the investigator:

- From signing the informed consent onwards until an individual subject's end of trial:
  - All AEs (serious and non-serious) and all AESIs
  - The only exception to this rule are AEs (serious and non-serious) and AESIs in Phase I trials in healthy volunteers, when subjects discontinue from the trial due to screening failures prior to administration of any trial medication. In these cases, the subjects' data must be collected at trial site but will not be entered in the CRF or trial database and will not be reported in the CTR.

- After the individual subject's end of trial:
  - The investigator does not need to actively monitor the subject for AEs but should only report any occurrence of cancer and related SAEs and related AESIs of which the investigator may become aware of by any means of communication, e.g. phone call. Those AEs should, however, not be reported in the CRF.

#### **5.2.6.2.2 AE reporting to the sponsor and timelines**

The Investigator must report SAEs, AESIs, and non-serious AEs which are relevant for the reported SAE or AESI, on the BI SAE form via fax immediately (within 24 hours) to the sponsor's unique entry point (country specific contact details will be provided in the ISF). The same timeline applies if follow-up information becomes available. In specific occasions the Investigator could inform the sponsor upfront via telephone. This does not replace the requirement to complete and fax the BI SAE form.

With receipt of any further information to these events, a follow-up SAE form has to be provided. For follow-up information, the same rules and timeline apply as for initial information.

#### **5.2.6.2.3 Information required**

All (S)AEs, including those persisting after the individual subject's end of trial, must be followed up until they have resolved, have been sufficiently assessed as 'chronic' or 'stable', or no further information can be obtained.

#### **5.2.6.2.4 Pregnancy**

[figure not shown]
In rare cases, pregnancy might occur in a clinical trial. Once a subject has been enrolled in the clinical trial and has taken trial medication, the investigator must report any drug exposure during pregnancy in a trial participant immediately (within 24 hours) by means of Part A of the Pregnancy Monitoring Form to the sponsor's unique entry point.

Similarly, potential drug exposure during pregnancy must be reported if a partner of a male trial participant becomes pregnant. This requires a written consent of the pregnant partner.

The outcome of the pregnancy associated with the drug exposure during pregnancy must be followed up and reported to the sponsor's unique entry point on the Pregnancy Monitoring Form for Clinical Trials (Part B).

The ISF will contain the Pregnancy Monitoring Form for Clinical Trials (Part A and Part B) as well as non-trial specific information and consent for the pregnant partner.

As pregnancy itself is not to be reported as an AE, in the absence of an accompanying SAE and/or AESI, only the Pregnancy Monitoring Form for Clinical Trials and not the SAE form is to be completed. If there is an SAE and/or AESI associated with the pregnancy, an SAE form must be completed in addition.

## **5.6 OTHER ASSESSMENTS**

### **5.6.1 Tyramine challenge**

Tyramine challenge will be conducted predose (Day -10 to Day -1) and during steady state (Day 8 to Day 19 for Dose Group 3, Day 29 to Day 39 for Dose Groups 1 and 2).

Before start of the tyramine challenge, subjects have rested for at least 5 min in a supine position. Systolic and diastolic blood pressures (BP) will be measured by a blood pressure monitor (Mortara Surveyor S12). Blood pressure will be measured approximately every 5 minutes during the 35 minutes preceding tyramine administration to determine the baseline SBP, i.e. mean of 3 consecutive measurements with a maximum range of 10 mmHg. If a stable SBP will not be obtained within the 35 minutes, the mean of all 7 readings will be used as the baseline value.

After baseline SBP has been established, fasted subjects will receive a single oral dose of tyramine. Tyramine doses will be escalated from 10 mg to 700 mg QD (10, 25, 50, 100, 200, 300, 400, 500, 600, and 700) on a daily basis. After each tyramine administration blood pressure will be again measured beginning 5 minutes after tyramine dosing and approximately every 5 minutes thereafter for at least 2 hours and then approximately every 15 minutes for additional 2 hours. For each subject, the tyramine dose escalation will be stopped when an increase of systolic blood pressure (SBP)  $\geq$  30 mmHg for at least 3 consecutive measurements is measured (i.e. TYR30). Participants who will not attain the predefined target elevation in SBP within 4 hours after the highest tyramine dose (700 mg) will not be included in the study.

At steady state the tyramine challenge test will be repeated, starting with a lower tyramine dose of 5 mg in all dose groups. Further tyramine dose escalation is identical to the predose regimen, apart from an intermediate dose of 150 mg only exclusively in the phenelzine group. Subjects will continue with their assigned treatment (BI 1467335 or placebo, or phenelzine) which is administered simultaneously to the tyramine dose. For each subject, the tyramine dose escalation will be stopped as soon as TYR30 has been established (increase of SBP  $\geq$  30 mmHg for at least 3 consecutive measurements). In none of the subjects the tyramine dose will exceed 700 mg, even if TYR30 has still not been established.

## **5.7 APPROPRIATENESS OF MEASUREMENTS**

Tyrosine sensitivity factor (TSF) was shown to be a suitable tool for the assessment of drug induced MAO-A inhibition and has been considered appropriate for risk assessment ([R18-2841](#), [R19-1593](#)).

Proprietary confidential information © 2020 Boehringer Ingelheim International GmbH or one or more of its affiliated companies

All further measurements performed during this trial are standard measurements and will be performed in order to monitor subjects' safety in an appropriate way. The scheduled measurements will allow monitoring of changes in vital signs, standard laboratory values, and ECG parameters that might occur as a result of administration of trial medication. The safety assessments are standard, are accepted for evaluation of safety and tolerability of an orally administered drug, and are widely used in clinical trials.

## 6. INVESTIGATIONAL PLAN

### 6.1 VISIT SCHEDULE

Exact times of measurements outside the permitted time windows will be documented. The acceptable time windows for screening and the end of trial examination are provided in the [Flow Chart](#).

Study measurements and assessments scheduled to occur ‘before’ trial medication administration on Day 1 are to be performed and completed within a 3 h-period prior to the trial drug administration.

If scheduled in the [Flow Chart](#) at the same time as a meal, blood sampling, vital signs, and 12-lead ECG recordings have to be done first. Furthermore, if several measurements including venepuncture are scheduled for the same time, venepuncture should be the last of the measurements due to its inconvenience to the subject and possible influence on physiological parameters.

For planned blood sampling times, refer to the [Flow Chart](#). While these nominal times should be adhered to as closely as possible, the actual sampling times will be recorded.

If a subject misses an appointment, it will be rescheduled if possible. The relevance of measurements outside the permitted time windows will be assessed no later than at the Report Planning Meeting.

### 6.2 DETAILS OF TRIAL PROCEDURES AT SELECTED VISITS

#### 6.2.1 Screening period

After having been informed about the trial, all subjects will provide written informed consent in accordance with GCP and local legislation prior to enrolment in the study.

For information regarding laboratory tests (including drug and virus screening), ECG, vital signs, and physical examination, refer to [Sections 5.2.3 to 5.2.6](#). For the tyramine challenge (Visit 2, hospitalisation from Day -12 up to Day -2; see Flowchart), results of this test are mandatory for final inclusion.

#### 6.2.2 Treatment period

##### Dose Group 1 and 2 (BI 1467335 or placebo)

Each subject will receive a single dose of BI 1467335 or placebo from Day 1 to Day 28.

On Days 2 to 6, 8 to 14, 15 to 20 and 22 to 25, subjects are allowed to take their study medication at home if deemed appropriate by the investigator. On Day 6, Day 13, Day 20 and Day 25 participants will be admitted to the trial site and, due to assessments and dispensing of study medication in the morning of the next day, will overnight at the trial site. From the evening of Day 25, subjects will stay hospitalized. Tyramine challenge will start from Day 29, with a maximum duration up to Day 39. As long as individual TYR30 has not been established subjects will continue their assigned study treatment (BI 1467335 or placebo).

Proprietary confidential information © 2020 Boehringer Ingelheim International GmbH or one or more of its affiliated companies

After TYR30 has been established, further treatment will be stopped and subjects are discharged from the study site.

### Dose Group 3 (phenelzine)

Subjects will be hospitalized during the complete treatment period, no ambulatory intake of study medication is planned. Each subject will receive 15 mg phenelzine BID (daily dose 30 mg) from Day 1 to Day 7. Tyramine challenge will start from Day 8, and will not exceed Day 19. Subjects will continue treatment with phenelzine up to TYR30 has been established. After TYR30 has been established, further treatment will be stopped and subjects are discharged from the study site.

For details on time points and procedures for collection of plasma samples for PK analysis, refer to [Flow Chart](#) and [Section 5.3.2](#).

The safety measurements performed during the treatment period are specified in [Section 5.3](#) of this protocol and in the [Flow Chart](#). For details on times of all other trial procedures, refer to the [Flow Chart](#). AEs and concomitant therapy will be assessed continuously from screening until the end of trial examination.

### 6.2.3 Follow-up period and trial completion

For AE assessment, laboratory tests, recording of ECG and vital signs, and physical examination during the follow-up period, see [Sections 5.2.2](#) to [5.2.5](#). Subjects who discontinue treatment before the end of the planned treatment period should undergo the EoTrial Visit.

All abnormal values (including laboratory parameters) assessed as clinically relevant by the investigator will be monitored using the appropriate tests until a return to a medically acceptable level is achieved. (S)AEs persisting after a subject's EoTrial Visit must be followed until they have resolved, have been sufficiently characterised, or no further information can be obtained.

Proprietary confidential information © 2020 Boehringer Ingelheim International GmbH or one or more of its affiliated companies

## 7. STATISTICAL METHODS AND DETERMINATION OF SAMPLE SIZE

### 7.1 STATISTICAL DESIGN – MODEL

The main objective of this trial is to compare the primary endpoint tyramine sensitivity factor (ratio of TYR30 at steady state compared to TYR30 at baseline) as listed in [Section 2.1.2](#) between the different treatment arms (BI 1467335 10mg, 15mg, Placebo and Phenelzine).

The trial will be evaluated statistically by use of a linear model for the logarithmically transformed endpoint.

The assessment of safety and tolerability is a further objective of this trial, and will be evaluated by descriptive statistics for the parameters specified in [Section 2.2.2.2](#).

### 7.2 NULL AND ALTERNATIVE HYPOTHESES

The TSF between the treatments BI 1467335 10mg (T1), BI 1467335 15mg (T2), placebo (R) and Phenelzine (C) will be compared. Ratios of geometric means (T1/R), (T2/R) and (C/R), and their corresponding 2-sided 90% confidence intervals (Cis) will be provided.

This method corresponds to the two one-sided t-test procedure, each at the 5% significance level. Since the main focus is on estimation and not testing, a formal hypothesis test and associated acceptance range is not specified.

### 7.3 PLANNED ANALYSES

#### Analysis sets

Statistical analyses will be based on the following analysis sets:

- Treated set (TS): The treated set includes all subjects who were randomized and treated with at least one dose of study drug. The treated set will be used for safety analyses.
- Per protocol analysis set (PPS): This set includes all subjects in the treated set (TS) who provide at least one endpoint that was defined as primary and was not excluded due to a protocol violation relevant. Descriptive and model based analyses of the primary endpoint will be based on the PPS.

Proprietary confidential information © 2020 Boehringer Ingelheim International GmbH or one or more of its affiliated companies

Adherence to the protocol will be assessed by the trial team. Important protocol deviations (IPD) categories will be suggested in the IQRM, IPDs will be identified no later than in the Report Planning Meeting, and the IPD categories will be updated as needed.

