### **7.3.1 Primary endpoint analyses**

#### Primary analyses

Descriptive statistics for the primary endpoint TSF will be presented.

The statistical model used for the analysis of the primary endpoint will be an analysis of variance (ANOVA) model on the logarithmic scale for each treatment relative to placebo. That is, the TSF will be log-transformed (natural logarithm) prior to fitting the ANOVA

Proprietary confidential information © 2020 Boehringer Ingelheim International GmbH or one or more of its affiliated companies

model. This model will include the fixed effect treatment (T1 and T2: treatment group, R: placebo, C: Phenelzine). The model is described by the following equation:

$$y_k = \mu + \tau_k + e_k, \text{ where}$$

$y_k$  = logarithm of response measured on treatment k,

$\mu$  = the overall mean,

$\tau_k$  = the  $k^{\text{th}}$  treatment effect,  $k = 1, 2, \dots$ ,

$e_k$  = the random error term,

where  $e_k \sim N(0, \sigma^2)$  i.i.d..

Point estimates for the ratios of the geometric means (T1/R), (T2/R) and (C/R) and corresponding two-sided 90% confidence intervals (CIs) will be provided.

For TSF the difference between the expected means for log(test)-log(reference) will be estimated by the difference in the corresponding adjusted means (Least Squares Means). Additionally their two-sided 90% confidence intervals will be calculated based on the residual error from the ANOVA and quantiles from the t-distribution. These quantities will then be back-transformed to the original scale to provide the point estimate and 90% CIs for each endpoint.

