## **7.5 HANDLING OF MISSING DATA**

### **7.5.1 Safety**

It is not planned to impute missing values for safety parameters.

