## 6. GENERAL ANALYSIS DEFINITIONS

### 6.1 TREATMENTS

For basic study information on treatments to be administered, assignment of treatment groups, and selection of doses, cf. Section 4 of the CTP.

All subjects will start by undergoing a "baseline" tyramine challenge receiving escalating daily doses of 5-700 mg tyramine until baseline TYR30 is reached. Baseline TYR30 is the tyramine dose causing an increase of systolic BP (SBP)  $\geq 30$  mmHg for at least 3 consecutive measurements compared with baseline SBP (baseline SBP is defined in [Section 6.6](#)).

Each subject is then planned to be treated with multiple doses of 10 mg or 15 mg BI 1467335 or matching placebo up to 39 days or with phenelzine up to 19 days. Treatment is to be stopped once TYR30 at steady state is achieved. Therefore, starting on Day 29 for BI 1467335 and placebo arms and on Day 8 for phenelzine, the tyramine challenge is to be repeated until TYR30 at steady state is reached.

For statistical analyses of AEs the following separate analysis phases will be defined for each subject:

Table 6.1: 1 Analysis phases for statistical analysis of AEs

Study analysis phase	Label	Start (inclusive)	End (exclusive)
Screening	Screening	Date of informed consent	Date/time of first administration of tyramine during Visit 2
On-treatment Tyramine screening challenge	Tyr screening	Date/time of first administration of tyramine during Visit 2	Date/time of first administration of BI 1467335, placebo or phenelzine respectively
On-treatment BI, Placebo or phenelzine	Placebo, 10 mg BI, 15 mg BI or Phen, respectively	Date/time of first administration of BI 1467335, placebo or phenelzine respectively	Date/time of first administration of tyramine during Visit 3 or 12:00 a.m. on day after last contact date whatever comes first
On-treatment BI + tyramine, Placebo + tyramine or phenelzine + tyramine	Placebo + Tyr, 10 mg BI + Tyr, 15 mg BI + Tyr or Phen + Tyr respectively	Date/time of first administration of tyramine during Visit 3	12:00 a.m. on day after last contact date

AE displays in CTR Section 15.3, Appendix 16.1.13.1.8.2 and Appendix 16.1.13.1.8.3 will present results for the on-treatment phase only.

In AE tables in CTR Section 15.3 (but not in Appendix 16.1.13.1.8.2 and Appendix 16.1.13.1.8.3 AE tables), the following totals will be provided in addition:

- **"Total on-trt"**, defined as the total over all on-treatment phases

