## **6.6 HANDLING OF MISSING DATA AND OUTLIERS**

Data of screened subjects who were withdrawn from the trial prior to first administration of any study drug will not be reported in the CTR.

Data of subjects who failed to complete all periods of the study (dropouts or withdrawals) will be reported in the CTR as far as their data are available. All withdrawals will be documented and the reason for withdrawal reported in the CTR.

**CTP:** *It is not planned to impute missing values for safety parameters.*

One exception where imputation might be necessary for safety evaluation are AE dates. Missing or incomplete AE dates are imputed according to BI standards [\(3\)](#).

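### No visible text says how a subject who reaches 700 mg at steady state without TYR30 enters TSF. The likely default, dropping them, pulls the 10 mg/placebo ratio toward 1 if BI 1467335 truly raises tyramine sensitivity.

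*Protocol*

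**What the plan says.** - **The case is foreseen.** Protocol 5.6.1 on the steady-state challenge: "In none of the subjects the tyramine dose will exceed 700 mg, even if TYR30 has still not been established".
- **TSF needs two TYR30 values.** Protocol 2.1.2 and SAP 5.1 define it as a ratio of TYR30 at baseline and at steady state, so without a steady-state TYR30 it is undefined.
- **SAP 6.1** gives a 5-700 mg range for the baseline challenge. For steady state it says only that "the tyramine challenge is to be repeated until TYR30 at steady state is reached", with nothing on a subject who does not reach it.
- **Missing data.** Protocol 7.5.1: "It is not planned to impute missing values for safety parameters". SAP 6.6 repeats this, adds "One exception where imputation might be necessary for safety evaluation are AE dates", and reports dropouts as far as data exist. A subject who finishes the challenge at 700 mg is not a dropout.
- **Analysis set.** Protocol 7.3 limits the per-protocol set to treated subjects "who provide at least one endpoint that was defined as primary and was not excluded due to a protocol violation relevant", and "Descriptive and model based analyses of the primary endpoint will be based on the PPS". TSF is the only primary endpoint.
- **Model.** Under Protocol 7.3.1 "the TSF will be log-transformed (natural logarithm) prior to fitting the ANOVA", with treatment as the only effect. SAP 7.4.1 keeps this model for 10 mg, phenelzine and placebo.
- **Summaries.** SAP 7.4.2 summarises steady-state TYR30, and SAP 7.8.3 the SBP rise at TYR30. Neither mentions non-reachers.
- **Inference.** Protocol 7.2: "Since the main focus is on estimation and not testing, a formal hypothesis test and associated acceptance range is not specified".

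**The concern.** A subject who tolerates 700 mg without the SBP rise is informative: the steady-state TYR30 is known to lie above 700 mg. If such subjects have no TSF and drop out, the analysis loses its least sensitive outcomes. Under no drug effect both arms lose the same share. If BI 1467335 raises sensitivity, placebo loses more, the remaining placebo subjects look more sensitive than they should, and the 10 mg/placebo ratio moves toward 1.

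That favours the conclusion the trial seeks. Protocol 1.3 wants to show no effect on intestinal MAO-A, so that dietary restrictions are unnecessary. After early termination this rests on the 10 mg group alone (SAP 4). With no acceptance range, readers will rely on the estimate and its harm-side 90% limit, which are the quantities that move. Without a written rule, the choice between dropping, entering 700 mg and censoring falls to sponsor staff, who are unblinded (Protocol 4.1.5).

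**Working it through.** **1. The plan's own figure.** Protocol Table 7.7: 1 uses gCV 86% and 16 v 16.
- Log SD = √ln(1 + 0.86²) = 0.744.
- ω = t(0.95; 30) × 0.744 × √(2/16) × √(χ²(0.95; 30)/30) = 0.539.
- Precision = exp(0.539) = 1.715, with limits 58.31% and 171.49% at ratio 100%. This matches the table, which assumes that all 32 subjects have a TSF.

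**2. Inputs for the size of the shift.** From the documents: the dose grids, the 700 mg cap, exclusion of baseline non-reachers, and exclusion of baseline TYR30 below 200 mg. That last rule is stated only in footnote 7 of the BI 1467335/placebo flow chart.

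Assumed, because the documents give no TYR30 distribution or non-attainment rate:
- lognormal TYR30 with median 300, 400 or 500 mg;
- between-subject log SD 0.4;
- test-retest log SD 0.2, 0.35 or 0.53. The last is 0.744/√2 = 0.526, borrowed from phenelzine; placebo may vary less.

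**3. Method.** Recorded TYR30 is the lowest grid dose at or above the simulated threshold. The steady-state threshold in the test arm is divided by the underlying ratio (1.0, 1.5 or 2.0). TSF is taken as baseline/steady state. There were 2,000,000 simulated subjects per arm before the baseline restriction.

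Shift = 1 − (T1/R with non-reachers dropped) / (T1/R on the same grid continued above 700 mg).

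This reference nets out the coarse grid, which by itself turns an underlying 2.0 into about 1.8.

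**4. Results when non-reachers are dropped.**

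| Median (mg) | Test-retest SD | Placebo loss | Shift at ratio 1.5 / 2.0 |
|---|---|---|---|
| 300 | 0.2 | 1.7% | 0.6 / 0.6% |
| 300 | 0.35 | 4.2% | 2.2 / 2.5% |
| 300 | 0.53 | 8.8% | 5.5 / 7.1% |
| 400 | 0.2 | 5.1% | 1.6 / 1.8% |
| 400 | 0.35 | 9.9% | 4.5 / 5.4% |
| 400 | 0.53 | 16% | 8.3 / 11.2% |
| 500 | 0.2 | 9.9% | 3.0 / 3.3% |
| 500 | 0.35 | 17% | 6.9 / 8.6% |
| 500 | 0.53 | 24% | 11.0 / 15.0% |

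At ratio 1 the shift is zero within simulation error in all nine settings. Loss alone does not fix the shift: at 9-10% placebo loss it ranges from about 3% to 7%. Removing the 200 mg baseline rule changes no shift by more than 0.6 points.

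**5. A second set of assumptions** (between-subject log SD 0.30).
- Median 400, test-retest SD 0.30, ratio 1.5: 1.416 on the uncapped grid, 1.371 dropped. Shift = 1 − 1.371/1.416 = 3.2%. Entering 700 mg gives 1.394, or 1.6%.
- Median 500, test-retest SD 0.526, ratio 2.0: 1.824 uncapped, 1.540 dropped. Shift = 1 − 1.540/1.824 = 15.6%. Entering 700 mg gives 1.664, or 8.8%.

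**6. Other rules, in the settings of step 4.** Entering 700 mg leaves 0.3 to 8.7%. Right-censored normal regression on treatment and log baseline stays within about 2% of the reference. At ratio 1.5 it leaves 0.1 to 1.5%, while the same covariate model fitted to completers only leaves 0.7 to 12.3%. So the censoring removes the bias, not the covariate.

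**7. How likely the case is.** The chance of at least one non-reacher among 16 placebo subjects runs from 1 − (1 − 0.017)^16 = 0.24 to 1 − (1 − 0.24)^16 = 0.99. If only 8 placebo subjects have a TSF, it is 0.13 to 0.89. The figure of 8 is an assumption, prompted by the early stop of the 15 mg group.

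**8. Orientation.** Protocol 7.1 and the synopsis methods word TSF as steady state over baseline. Protocol 3.2 and Table 7.7: 1 imply the inverse. The move toward 1 holds under both.

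**The case against.** The strongest case against has four parts.

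**Silence is weak evidence here.** Parts of the SAP are redacted or not shown, and the ADS Plan it cites was not supplied. A rule could sit there. This stands: the point is limited to visible text. A reader might infer that the plan excludes non-reachers. It does not say so; exclusion is inferred from the per-protocol wording, and a programmer could equally enter 700 mg. A reader might also infer that the SAP ignores the 700 mg limit. It does not, because SAP 6.1 gives the range for the baseline challenge. What is missing is the steady-state outcome.

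**The size is assumed.** Protocol 4.1.2 expects enough subjects to attain TYR30, and screening removes anyone above 700 mg at baseline. The 11-15% shift comes from one corner that uses a phenelzine-derived SD. This also stands. Screening does not, however, stop a subject with a high baseline TYR30 from exceeding 700 mg on retest.

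**Nothing formal is broken.** The trial is exploratory, with no test or margin. A reader might infer that the plan favours a no-effect result in every case, or invalidates it. The documents do not support that: there is no bias when the true ratio is 1, and no decision rule exists to be violated.

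**Losses would be partly visible.** Listings and N per arm (SAP 7, 7.4.2, 7.8.3) would show missing TSF values. They would not separate non-reachers from dropouts or correct the estimate.

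**Conclusion.** The gap holds for the visible text. The plan foresees the non-reacher and gives no rule, and its most natural reading drops that subject. The direction is firm: toward no effect if BI 1467335 raises sensitivity, and no bias if it does not. The size is illustrative only. At underlying ratios of 1.5 to 2.0 it is about 0.6 to 3% when test-retest log SD is 0.2, and reaches 11 to 15% only with median 500 mg and SD 0.53. These figures rest on lognormal TYR30 and on inputs that the documents do not supply. This should be fixed, with medium confidence; it is not a fatal flaw.

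**What to change.** In SAP 5.1, 6.3, 6.6 and 7.4:

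1. Keep subjects who complete the steady-state challenge to 700 mg without TYR30 in the primary-endpoint set, recorded as right-censored at > 700 mg.
2. Keep the protocol ANOVA and state how it treats these subjects. If it leaves them out, label it a completer analysis.
3. Report beside it a right-censored normal regression of log steady-state TYR30 on treatment and log baseline TYR30, with 90% CI. With log baseline in the model, the treatment effect on log(baseline/steady state) is exactly minus the effect on log steady-state TYR30.
4. Add a completer fit of the same covariate model, so that the effect of censoring can be separated from that of the covariate.
5. Tabulate non-reachers per arm, separately from dropouts.
6. State how they enter the summaries in SAP 7.4.2 and 7.8.3.

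The SAP was finalised after the trial had stopped, so this should be specified before TSF is derived or labelled post hoc. Separately, reconcile the TSF orientation between Protocol 7.1 (and the synopsis) and Protocol 3.2 with Table 7.7: 1.

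Cost: a few sentences, one count per arm and one standard procedure (for example PROC LIFEREG), with no new data. The downside is minor programming and a normality assumption for the unobserved tail.
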